15.4. Appendix 4: Response Criteria

Non-Hodgkin's Lymphoma Response Criteria

This study employs response criteria from the Revised Response Criteria for Malignant Lymphoma (RRCML), [Cheson, 2007]. These criteria use the following categories of response: CR, PR, Stable Disease (SD), Relapse and Progression. Because the criteria for PR requires a decrease by $\geq 50\%$ in sum of products of the diameters (**SPD**) in the six largest dominant nodes or nodal masses, six dominant nodes and/or nodal masses must be identified if $>$ six involved nodes/nodal masses are present.

Complete Response

To be assigned a status of complete response, all changes must be confirmed by repeat assessments performed no less than four weeks after the criteria for CR were met.

1. Complete disappearance of all detectable clinical evidence of disease and disease related B-symptoms, if present prior to therapy.
2. All lymph nodes and nodal masses must have regressed on CT to normal size. Nodes that were 1.1 to 1.5 cm in their longest diameter and more than 1.0 cm in their shortest diameter prior to treatment must have decreased to ≤ 1.0 cm in their shortest diameter. Nodes that were > 1.5 cm in their longest diameter prior to therapy must have decreased to ≤ 1.5 cm in the longest diameter.
3. The spleen and/or liver, if considered to be enlarged due to lymphoma before therapy on the basis of a CT scan, should be considered normal size by imaging studies, and nodules related to lymphoma should disappear. However, determination of splenic involvement is not always reliable because spleen considered normal in size may still contain lymphoma, whereas an enlarged spleen may reflect variations in anatomy, blood volume, the use of hematopoietic growth factors, or causes other than lymphoma.
4. If the bone marrow was involved by lymphoma prior to treatment, the biopsy must be cleared. The biopsy sample on which this determination is made must be adequate (with a goal of > 20 mm unilateral core). If the sample is indeterminate by morphology, it should be negative by immunohistochemistry. A sample that is negative by immunohistochemistry but that demonstrates a small population of clonal lymphocytes by flow cytometry will be considered a CR until data become available demonstrating a clear difference in subject outcome.

Partial Response

To be assigned a status of partial response, all changes must be confirmed by repeat assessments performed no less than four weeks after the criteria for PR were met.

1. At least a 50% decrease from baseline in the SPD of up to six of the largest dominant nodes or nodal masses.

2. No increase in the size of the liver or the spleen. No unequivocal progression in any nonmeasurable or nondominant site.
3. Splenic and hepatic nodules must regress by $\geq 50\%$ in SPD compared to baseline. If only a single nodule/lesion, it must regress by $\geq 50\%$ in the greatest transverse diameter compared to baseline.
4. With the exception of splenic and hepatic nodules, involvement of other organs is accessible and no measureable disease should be present.
5. Bone marrow assessment is not relevant for determination of a PR if the sample was positive prior to treatment. However, if positive, the cell type should be specified. Subjects who achieve CR criteria above, except for persistent morphologic bone marrow involvement will be considered partial responders. When the bone marrow was involved before therapy and a clinical CR was achieved, but no bone marrow assessment after therapy, subjects must be considered partial responders.
6. No new sites of disease must be observed.
7. When performed, positron emission tomography (PET) must be positive in at least one previously involved site.

Stable Disease

Neither sufficient shrinkage to qualify for a CR or PR nor sufficient increase to qualify for progressive disease taking as reference the smallest SPD since the treatment started.

When performed, PET should be positive at prior sites of disease with no new areas of involvement on the CT or PET.

Relapsed Disease (after CR)/Progressive Disease (after PR, SD)

Criteria for determining PD for new lesions and target lesions are shown in [Table 19](#):

Table 19 Criteria for determining PD for new lesions and target lesions

	Nodes	Extranodal ('liver/spleen' & 'other' categories)
New node/lesion^c	
A node that was normal ($\leq 1.5 \times \leq 1.0$cm, including nodes that were not previously visible) and PET negative at baseline, must increase to $> 2.0 \times \geq 1.5$ cm. The new lesion must not be attributable to non-lymphoma-related causes.
 
If PET is performed, the lesion must be PET positive.
	
An unequivocal new lesion at a site where there was no disease at baseline (including being PET negative), provided the lesion cannot be attributed to non-lymphoma-related causes.
 
If PET is not performed the new lesion must be > 1.5cm in the long axis^a.
 
If PET is performed, the lesion must be PET positive.

Single target node/lesion		
Increase in product of the perpendicular diameters (PPD)	$\geq 50\%$ increase from nadir in the PPD of any baseline dominant node. The long axis must increase by at least 5mm and to > 2.0 cm.	$\geq 50\%$ increase from nadir in the PPD of any baseline dominant target lesion, and at least a 5mm increase in either of the axes, and the lesion must be

	Nodes	Extranodal ('liver/spleen' & 'other' categories)
	If PET is performed, the lesion must be PET positive.	>1.5cm x ≥1.5 cm. If PET is performed, the lesion must be PET positive.
Increase in long axis	≥50% increase from nadir in the long axis of any baseline dominant node. The long axis must increase by at least 5mm and to >2.0 cm. If PET is performed, the lesion must be PET positive.	≥50% increase from nadir in the long axis of any baseline dominant lesion, and at least a 5mm increase in the long axis, and the lesion must be >1.5cm x ≥1.5cm. If PET is performed, the lesion must be PET positive.
Multiple target nodes/lesions		
Increase in SPD	≥50% increase from nadir in the SPD of baseline dominant nodes and at least one node should have a long axis >1.5cm^b. If PET is performed, nodes >1.5cm must be PET positive.	≥50% increase from nadir in the SPD of baseline dominant lesions and at least one lesion should have a long axis >1.5cm^b. If PET is performed, lesions >1.5cm must be PET positive.

- a. Due to the resolution of PET imaging, requiring a lesion to be PET positive will normally mean it will be at least 1.5cm. To ensure consistency when PET is not performed a minimum lesion size of >1.5cm is required.
- b. Requiring that at least one lesion is >1.5cm minimises the risk of declaring PD based on small artefactual changes and allows for the introduction of PET positivity for declaring PD (when PET is performed).
- c. Abnormal nodes/extranodal lesions present at baseline that normalise/resolve and then subsequently enlarge/relapse are not to be classified as new lesions.

Response Assessment

CT scans remain the standard for evaluation of nodal disease. Chest, abdominal, and pelvic CT scans should be done even if those areas were not initially involved because of the unpredictable pattern of relapse in NHL. Neck can be evaluated if present at baseline.

References:

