Tumor biopsy for PD optional for Part 1 and Part 2. Required for PK/PD cohort	A tumor biopsy should be obtained at D1 (up to -14 days) and after 6 th dose Day 18(+3 day window)		X		X (After 6 th dose, Day 18) ^h			
Tumor biopsy for biomarker research	Recommended for all subjects							X (at progression)
Additional Assessments for PD/PK Cohort ^m								
Blood for metabolite evaluation (Part 2 PK/PD expansion cohort only)			Day 1 (Table 7)		Day 15 (Table 7)			
Urine for Metabolite (Part 2 PK/PD expansion cohort only)	On Day 15, urine samples should be collected while subject is in the office		Day 1 prior to first dose and from 0 to 24h		Day 15 from 0 to 8 h			

	STUDY PHASE	SCREEN	First Treatment Period Cycle 1			Day 21	Continuation Phase Cycle 2 and beyond	Follow-Upⁱ
			Day 1 and 4^a	Day 8 and 11^a	Day 15 and 18^a			
	VISIT	Screen						
	VISIT WINDOW (\pmdays)		-14				$\pm 7^l$	$\pm 7^l$
Bile for metabolite (Part 2 PK/PD expansion cohort only) – at least 4 subjects)					Day 15			
Plasma for 4 β -hydroxycholesterol and cholesterol assay (Part 2 PK/PD expansion cohort only)			X (Day 1 prior to First Dose)			X		
Disease Assessments for Lymphoma Subjects: Baseline disease assessments at screening and repeated 8 weeks after dosing is initiated and every 12 weeks thereafter								
Computed Tomography (CT) ^k	Must be completed within 4 weeks of first dose of GSK2816126 and repeated 8 weeks after dosing is initiated. Every 12 weeks thereafter	X					X	X ^d

	STUDY PHASE	SCREEN	First Treatment Period Cycle 1			Day 21	Continuation Phase Cycle 2 and beyond	Follow-Up ^j
			Day 1 and 4 ^a	Day 8 and 11 ^a	Day 15 and 18 ^a			
	VISIT	Screen						
	VISIT WINDOW (\pmdays)	-14					$\pm 7^l$	$\pm 7^l$
Positron emission tomography (PET)	The use of standalone PET or PET in combination with CT scan is optional. Standalone PET does not replace CT	X ^e					X ^e	X ^{d,e}
Bone Marrow biopsy	See Section 7.7	X					X ^f	X ^f
B symptoms	See Section 7.7	X	X	X	X	X	X	
Disease Assessments for Multiple Myeloma (MM) subjects: Baseline disease assessments at screening, week 4 and then every 6 weeks thereafter unless otherwise noted								
Disease Characteristics	Every 6 weeks after Wk4, Including cytogenetics as appropriate	X					X	
Total Protein, CRP, β 2 microglobulin	Every 6 weeks after Wk4	X					X	
Response Assessment	Every 6 weeks after Wk4; Response criteria in Appendix 6						X	

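### Appendix 4 leaves a lymphoma subject with at least a 50% SPD decrease, a node still above the CR size limit and a negative PET in no response category, so the ORR depends on whether the optional PET was done

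*Protocol*

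**What the plan says.** All of the response wording is in Protocol Section 15.4, Appendix 4.

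- **CR, item 2:** "All lymph nodes and nodal masses must have regressed on CT to normal size". For larger nodes the limit is explicit: "Nodes that were > 1.5 cm in their longest diameter prior to therapy must have decreased to ≤ 1.5 cm in the longest diameter". None of the four CR items mentions PET.
- **PR, item 1:** "At least a 50% decrease from baseline in the SPD of up to six of the largest dominant nodes or nodal masses".
- **PR, item 7:** "When performed, positron emission tomography (PET) must be positive in at least one previously involved site".
- **SD:** defined by too little shrinkage for CR or PR and too little growth for progression, and then: "When performed, PET should be positive at prior sites of disease with no new areas of involvement on the CT or PET".
- **Response Assessment paragraph:** "CT scans remain the standard for evaluation of nodal disease".

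The lymphoma block of Table 6 (Section 7.1) says of PET: "The use of standalone PET or PET in combination with CT scan is optional. Standalone PET does not replace CT". Footnote e to that table prefers diagnostic CT and lets the investigator choose PET/CT instead.

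The investigator assigns lymphoma response by Appendix 4 (Section 7.7), and Section 12.3.5.4 bases the efficacy analysis on the same appendix. ORR, as CR plus PR, is the Part 2 primary endpoint (Section 2.2). It also drives the futility and efficacy rule of the Part 1 GCB-DLBCL expansion (Sections 3.3.7 and 12.2.1.2).

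**The concern.** The CR list relies on CT alone, while the PR and SD texts add a PET condition that applies only if the scan happens to be done. PR item 7 is coherent only if a PET-negative subject with a residual mass is placed somewhere else, and in this appendix that subject has no other place.

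The count of responders then depends on local imaging practice. Two subjects with identical CT findings can contribute differently to the ORR because one site used PET/CT and the other did not.

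The stopping tables turn on single subjects. In Table 16, 2 responders of 13 meet the futility threshold and 3 do not; at 27 subjects, 8 is futility and 9 is efficacy. In Table 17, 9 of 32 is futility and 10 is not. Lymphoma subjects treated at the MTD/RP2D in Part 1 are also carried into the Part 2 analysis (Section 3.4), so a scoring difference in Part 1 would carry forward.

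**Working it through.** **Step 1. Put one subject through the criteria.** Take a lymphoma subject whose SPD has fallen by at least 50%, with one node still above 1.5 cm that was above 1.5 cm before therapy, no new disease, all other PR items met and the response confirmed.

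| Category | PET not done | PET done and negative |
|---|---|---|
| CR | Fails item 2 (node above size limit) | Fails item 2; no PET route exists |
| PR | Met; item 7 does not apply | Fails item 7 |
| SD | Does not fit; shrinkage is enough for PR | Does not fit; shrinkage is enough and PET is not positive at prior sites |
| Progression | No | No |
| Counted in ORR | Yes, as PR | No category, so not counted |

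PR item 5 does not help. It covers subjects who meet CR except for bone marrow findings, not those with a residual node. If the node has shrunk to within the CR limit, the problem does not arise.

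**Step 2. Reproduce the stated operating characteristics.** The inputs are the Table 16 boundaries (looks at n = 13 to 27, futility and efficacy) and the Table 17 boundaries (n = 10 to 32, futility only), with one look after each subject.

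Let f(n, k) be the probability of being still enrolling with k responders after n subjects. Then f(n, k) = f(n−1, k)(1−p) + f(n−1, k−1)p, and probability is removed at each look where k reaches a boundary. Power is the total probability of crossing the efficacy boundary or of ending above the futility number at the maximum n.

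| Design | Quantity | Stated | Recomputed |
|---|---|---|---|
| Part 1, Table 16 | Type I error, p = 0.20 | 0.087 | 0.0865 |
| | Power, p = 0.40 | 0.803 | 0.8031 |
| | Expected n (null / alternative) | 16.48 / 16.98 | 16.48 / 16.98 |
| Part 2 lymphoma, Table 17 | Type I error, p = 0.20 | 0.066 | 0.0660 |
| | Power, p = 0.40 | 0.801 | 0.8007 |
| | Expected n (null / alternative) | 16.06 / 29.16 | 16.06 / 29.16 |

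The plan's own figures are reproduced.

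**Step 3. Illustrate the loss.** Let m be the share of would-be responders who are PET-scanned, PET-negative and left with a node above the CR limit. The documents give no value for m, so every row except the first is an assumption. The scored rate is 0.40 × (1 − m); for example, 0.40 × 0.90 = 0.36.

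| m (assumed) | Scored ORR | Power, Part 1 | Power, each Part 2 lymphoma cohort |
|---|---|---|---|
| 0 | 40% | 0.803 | 0.801 |
| 1% | 39.6% | 0.792 | 0.789 |
| 2% | 39.2% | 0.780 | 0.778 |
| 3% | 38.8% | 0.768 | 0.766 |
| 5% | 38% | 0.743 | 0.740 |
| 10% | 36% | 0.674 | 0.668 |
| 20% | 32% | 0.513 | 0.501 |

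**Step 4. Direction.** The same loss at a true 20% lowers the type I error. With m = 10% the scored rate is 18%, and the error falls from 0.087 to 0.052 in Part 1 and from 0.066 to 0.036 in Part 2.

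**The case against.** **No text calls this subject a non-responder.** The subject is unclassified, and since CT is named as the standard for nodal disease, an investigator could let CT govern and record PR. That is fair, and a reader should not infer that the protocol deliberately scores these subjects as SD or treatment failure. But recording PR would mean disregarding item 7, which is mandatory in form. If some sites do so and others do not, scoring still differs by site.

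**The cited published criteria or the analysis plan may settle the case.** Neither is at hand. Appendix 4 writes out its own items and is the text that investigators are told to apply, so it should be consistent in itself.

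**Nothing ranks these subjects as the strongest responders.** This is correct. It is tempting to say that the rule discards the best responses, but no passage places a PET-negative residual node above a PET-positive PR. The point does not need that claim.

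**The power figures have no documentary basis.** This stands in part. The affected share requires PET to be done, to be negative, and a node to remain above the limit; PET is optional and CT preferred. Shares of 1% to 3% are as compatible with the documents as 10% or 20%, and they leave power at about 0.77 to 0.79. ORR is also defined by these same criteria, and nothing shows that the 40% alternative was set under a more generous rule.

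**Decisions are not mechanical.** Crossing futility means a cohort may be stopped on the totality of the data (Section 3.3.7), and scans are stored centrally with independent review possible (Section 11). This softens the effect on decisions but does not repair the endpoint definition.

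**Conclusion.** The gap is real and follows from the appendix text alone. A lymphoma subject who meets every PR criterion except item 7, with a node above the CR limit and a negative PET, belongs to no response category. The ORR therefore depends on whether an optional scan was done. It concerns the primary endpoint in four Part 2 cohorts and the Part 1 GCB-DLBCL decision rule.

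Its size is unknown. The illustrative power range runs from about 0.79 at a 1% loss to about 0.5 at 20%. It assumes that the design's 40% describes the rate before such losses and that losses fall evenly on would-be responders. It should not be read as an estimate of lost power. Nor should a reader infer a risk of false claims of efficacy, because the error is towards missing activity.

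A broader reading, that PET should never influence response status, is not supported. In Table 19 PET, if performed, bears on whether a new or enlarging lesion counts as progression, and nothing in this point calls that into question.

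**What to change.** Reconcile the CR, PR and SD items of Appendix 4:

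1. State that a negative PET alone does not prevent a subject who meets all other PR criteria from being counted as a responder in the ORR. The sponsor should say whether the label is CR or PR; the ORR is the same either way.
2. Amend the PET sentence under SD to match, so that the two categories do not conflict.
3. Leave the Table 19 PET rules for progression unchanged. Avoid a blanket statement that PET has no bearing on response status, since it would clash with that table.

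The cost is a few sentences in Appendix 4, the matching response programming and a note to sites. It needs no extra scans and no change to sample size or stopping boundaries. Responses already recorded in lymphoma subjects who had PET should be checked against the amended text before the cohorts are read.

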15.5. Appendix 5: RECIST 1.1

I. Efficacy Assessment

Disease progression and response evaluations will be determined according to the definitions established in the Response Evaluation Criteria in Solid Tumors (RECIST 1.1) [Chung, 2010; Eisenhauer, 2009].

See the Time and Events Table for the schedule of efficacy assessments. Assessments must be performed on a calendar schedule and should not be affected by dose interruptions/delays. For post baseline assessments, a window of ± 7 days is permitted to allow for flexible scheduling.

- The following are required at baseline: CT for Chest/Abdomen/Pelvis or MRI for Abdomen/Pelvis and clinical disease assessment for palpable lesions, brain scan and bone scan (bone scan as clinically indicated). At each post baseline assessment, evaluations of the sites of disease identified by these scans are required except for brain scan and bone scans. Brain and Bone scans should be performed as clinically indicated.

Confirmation of CR and PR are required per protocol. Confirmation assessments must be performed no less than 4 weeks after the criteria for response have initially been met and may be performed at the next protocol scheduled assessment. If a confirmation assessment is performed prior to the next protocol schedule assessment, the next protocol scheduled evaluation is still required (e.g. evaluations must occur at each protocol scheduled timepoint regardless of unscheduled assessments).

A baseline bone scan should be performed as clinically indicated. For subjects without bone disease at baseline, subsequent bone scans should only be performed as clinically indicated (e.g. presentation of bone pain). For subjects with bone disease at baseline, a bone scan is required as clinically indicated. In addition, in order to assign a response of CR in a subject with bone disease at baseline, a bone scan must be performed 1 week prior to 4 weeks after.

A baseline brain scan is required for all subjects. For subjects without CNS disease at baseline, subsequent brain scans should only be performed as clinically indicated (e.g. symptoms suggestive of CNS progression). For subjects with CNS disease at baseline, a brain scan is required as clinically indicated. In addition, in order to confirm a CR in a subject with brain disease at baseline, a brain scan must be performed 1 week prior to the 1st set of images showing CR to 4 weeks after the next protocol specified assessment.

Ia. Baseline documentation of target and non-target lesions

- All baseline lesion assessments must be performed within 28 days of randomizations.
- Lymph nodes that have a short axis of <10 mm are considered non-pathological and should not be recorded or followed.

- Pathological lymph nodes with <15mm and but ≥ 10 mm short axis are considered non measurable.
- Pathological lymph nodes with ≥ 15 mm short axis are considered measurable and can be selected as target lesions; however, lymph nodes should not be selected as target lesions when other suitable target lesions are available.
- Measurable lesions up to a maximum of 2 lesions per organ and 5 lesions in total, representative of all involved organs, should be identified as target lesions, and recorded and measured at baseline. These lesions should be selected on the basis of their size (lesions with the longest diameter) and their suitability for accurate repeated measurements (either by imaging techniques or clinically).

Note: Cystic lesions thought to represent cystic metastases should not be selected as target lesions when other suitable target lesions are available.

Note: Measurable lesions that have been previously irradiated and have not been shown to be progressing following irradiation should not be considered as target lesions.

- Lytic bone lesions or mixed lytic-blastic lesions, with identifiable soft tissue components, that can be evaluated by CT or MRI can be considered measurable. Bone scans, [18F]fluorodeoxyglucose (FDG)-PET scans or X-rays are not considered adequate imaging techniques to measure bone lesions.
- All other lesions (or sites of disease) should be identified as non-target and should also be recorded at baseline. Non-target lesions will be group by organ. Measurements of these lesions are not required, but the presence or absence of each should be noted throughout follow-up.

Ib. Assessment Guidelines

Please note the following:

- The same diagnostic method, including use of contrast when applicable, must be used throughout the study to evaluate a lesion.
- All measurements should be taken and recorded in millimeters (mm), using a ruler or calipers.
- Ultrasound is not a suitable modality of disease assessment. If new lesions are identified by ultrasound, confirmation by CT or MRI is required.
- Fluorodeoxyglucose (FDG)-PET is generally not suitable for ongoing assessments of disease. However FDG-PET can be useful in confirming new sites of disease where a positive FDG-PET scans correlates with the new site of disease present on CT/MRI or when a baseline FDG-PET was previously negative for the site of the new lesion. FDG-PET may also be used in lieu of a standard bone scan providing coverage allows interrogation of all likely sites of bone disease and FDG-PET is performed at all assessments.
- If PET/CT is performed then the CT component can only be used for standard response assessments if performed to diagnostic quality, which includes the required

anatomical coverage and prescribed use of contrast. The method of assessment should be noted as CT on the CRF.

Clinical Examination: Clinically detected lesions will only be considered measurable when they are superficial (e.g., skin nodules). In the case of skin lesions, documentation by color photography, including a ruler/callipers to measure the size of the lesion, is required. [Chung, 2010; Eisenhauer, 2009].

CT and MRI: Contrast enhanced CT with 5mm contiguous slices is recommended. Minimum size of a measurable baseline lesion should be twice the slice thickness, with a minimum lesion size of 10 mm when the slice thickness is 5 mm. MRI is acceptable, but when used, the technical specification of the scanning sequences should be optimized for the evaluation of the type and site of disease and lesions must be measured in the same anatomic plane by use of the same imaging examinations. Whenever possible the same scanner should be used. [Chung, 2010; Eisenhauer, 2009].

X-ray: In general, X-ray should not be used for target lesion measurements owing to poor lesion definition. Lesions on chest X-ray may be considered measurable if they are clearly defined and surrounded by aerated lung; however chest CT is preferred over chest X-ray [Chung, 2010; Eisenhauer, 2009].

Brain Scan: Baseline brain scans are required, then contrast enhanced MRI is preferable to contrast enhanced CT.

Bone Scan (typically bone scintigraphy): If a bone scan is performed and a new lesion(s) is equivocal, then correlative imaging (i.e. X-ray, CT, or MRI) is required to demonstrate malignant characteristics of the lesion(s).

Note: PET [FDG or fluoride] may be used in lieu of a standard bone scan providing coverage allows interrogation of all likely sites of bone disease and PET is performed at all assessments.

Ic. Follow-up Assessments for Subjects Permanently Discontinued from Study Treatment

Refer to Section 8.3.1.1 and the Time and Events Tables found in the protocol for follow-up assessment of subjects who are to be followed up for disease progression and/or survival after permanently discontinue from study treatment.

Id. Assessment of Subject Completion

If the last radiographic assessment was more than 8 weeks prior to withdrawal from study and progressive disease has not been documented, a disease assessment should be obtained at the time of withdrawal from study.

II. Guidelines for Evaluation of Disease

IIa. Measurable and Non-measurable Definitions

Measurable lesion:

A non nodal lesion that can be accurately measured in at least one dimension (longest dimension) of

- ≥ 10 mm with MRI or CT when the scan slice thickness is no greater than 5mm. If the slice thickness is greater than 5mm, the minimum size of a measurable lesion must be at least double the slice thickness (e.g., if the slice thickness is 10 mm, a measurable lesion must be ≥ 20 mm).
- ≥ 10 mm calliper/ruler measurement by clinical exam or medical photography.
- ≥ 20 mm by chest x-ray.

Additionally lymph nodes can be considered pathologically enlarged and measurable if

- ≥ 15 mm in the short axis when assessed by CT or MRI (slice thickness recommended to be no more than 5mm). At baseline and follow-up, only the short axis will be measured [Chung, 2010; Eisenhauer, 2009].

Non-measurable lesion:

All other lesions including lesions too small to be considered measurable (longest diameter <10 mm or pathological lymph nodes with ≥ 10 mm and <15 mm short axis) as well as truly non-measurable lesions, which include: leptomeningeal disease, ascites, pleural or pericardial effusions, inflammatory breast disease, lymphangitic involvement of the skin or lung, abdominal masses/abdominal organomegaly identified by physical exam that is not measurable by reproducible imaging techniques [Eisenhauer, 2009].

Measurable disease: The presence of at least one measurable lesion. Palpable lesions that are not measurable by radiologic or photographic evaluations may not be utilized as the only measurable lesion.

Non-Measurable only disease: The presence of only non-measurable lesions. Note: non-measurable only disease is not allowed per protocol.

III. Response Criteria

IIIa. Evaluation of target lesions

Definitions for assessment of response for target lesion(s) are as follows:

- Complete Response (CR): Disappearance of all target lesions. Any pathological lymph nodes must be <10 mm in the short axis.
- Partial Response (PR): At least a 30% decrease in the sum of the diameters of target lesions, taking as a reference, the baseline sum of the diameters (e.g. percent change from baseline).

- Stable Disease (SD): Neither sufficient shrinkage to qualify for PR nor sufficient increase to qualify for progressive disease.
- Progressive Disease (PD): At least a 20% increase in the sum of the diameters of target lesions, taking as a reference, the smallest sum of diameters recorded since the treatment started (e.g. percent change from nadir, where nadir is defined as the smallest sum of diameters recorded since treatment start). In addition, the sum must have an absolute increase from nadir of 5mm.
- Not Applicable (NA): No target lesions at baseline.
- Not Evaluable (NE): Cannot be classified by one of the five preceding definitions.

Note:

- If lymph nodes are documented as target lesions the short axis is added into the sum of the diameters (e.g. sum of diameters is the sum of the longest diameters for non-nodal lesions and the short axis for nodal lesions). When lymph nodes decrease to non-pathological size (short axis <10mm) they should still have a measurement reported in order not to overstate progression.
- If at a given assessment time point all target lesions identified at baseline are not assessed, sum of the diameters cannot be calculated for purposes of assessing CR, PR, or SD, or for use as the nadir for future assessments. However, the sum of the diameters of the assessed lesions and the percent change from nadir should be calculated to ensure that progression has not been documented. If an assessment of PD cannot be made, the response assessment should be NE.
- All lesions (nodal and non-nodal) should have their measurements recorded even when very small (e.g. 2 mm). If lesions are present but too small to measure, 5 mm should be recorded and should contribute to the sum of the diameters, unless it is likely that the lesion has disappeared in which case 0 mm should be reported.
- If a lesion disappears and reappears at a subsequent time point it should continue to be measured. The response at the time when the lesion reappears will depend upon the status of the other lesions. For example, if the disease had reached a CR status then PD would be documented at the time of reappearance. However, if the response status was PR or SD, the diameter of the reappearing lesion should be added to the remaining diameters and response determined based on percent change from baseline and percent change from nadir.

IIIb. Evaluation of non-target lesions

Definitions for assessment of response for non-target lesions are as follows:

- Complete Response (CR): The disappearance of all non-target lesions. All lymph nodes identified as a site of disease at baseline must be non-pathological (e.g. <10 mm short axis).
- Non-CR/Non-PD: The persistence of 1 or more non-target lesion(s) or lymph nodes identified as a site of disease at baseline \geq 10 mm short axis.
- Progressive Disease (PD): Unequivocal progression of existing non-target lesions.

- Not Applicable (NA): No non-target lesions at baseline.
- Not Evaluable (NE): Cannot be classified by one of the four preceding definitions.

Note:

- In the presence of measurable disease, progression on the basis of solely non-target disease requires substantial worsening such that even in the presence of SD or PR in target disease, the overall tumor burden has increased sufficiently to merit discontinuation of therapy.
- Sites of non-target lesions, which are not assessed at a particular timepoint based on the assessment schedule, should be excluded from the response determination (e.g. non-target response does not have to be "Not Evaluable").

IIIc. New lesions

New malignancies denoting disease progression must be unequivocal. Lesions identified in follow-up in an anatomical location not scanned at baseline are considered new lesions.

Any equivocal new lesions should continue to be followed. Treatment can continue at the discretion of the investigator until the next scheduled assessment. If at the next assessment the new lesion is considered to be unequivocal, progression should be documented.

IIId. Evaluation of overall response

The table below presents the overall response at an individual time point for all possible combinations of tumor responses in target and non-target lesions with or without the appearance of new lesions for subjects with measurable disease at baseline.

Evaluation of Overall Response for Subjects with Measurable Disease at Baseline

Target Lesions	Non-Target Lesions	New Lesions	Overall Response
CR	CR or NA	No	CR
CR	Non-CR/Non-PD or NE	No	PR
PR	Non-PD or NA or NE	No	PR
SD	Non-PD or NA or NE	No	SD
NE	Non-PD or NA or NE	No	NE
PD	Any	Yes or No	PD
Any	PD	Yes or No	PD
Any	Any	Yes	PD

CR=complete response, PR = partial response, SD=stable disease, PD=progressive disease, NA= Not applicable, and NE=Not Evaluable

Note:

- Subjects with a global deterioration of health status requiring discontinuation of treatment without objective evidence of disease progression at that time should be classified as having "symptomatic deterioration." Objective response status is determined by evaluations of disease burden. Every effort should be made to document the objective progression even after discontinuation of treatment.

- In some circumstances, it may be difficult to distinguish residual disease from normal tissue. When the evaluation of CR depends on this determination, it is recommended that the residual lesion be investigated (fine needle aspirate/biopsy) to confirm the CR.
- The dosing schedule, dosing interruptions and unique design (see [Table 2](#) of the protocol) should be considered when assessing tumor response. Thus, subjects with PD before Week 8, but without rapid clinical deterioration, may continue planned dosing schedule to allow detection of antitumor response. It is recommended that subjects who experience investigator-determined PD at the week 8, at the discretion of the investigator, may receive additional tumor assessment before the initiation of alternative anticancer therapy.
- During Part 1 or Part 2, is recommended that subjects who experience investigator-determined PD at any time, at the discretion of the investigator, may receive additional tumor assessment before the initiation of alternative anticancer therapy.

IIIe. Evaluation of best overall response

The best overall response is the best response recorded from the start of the treatment until disease progression/recurrence and will be determined programmatically by GSK based on the investigators assessment of response at each time point.

- To be assigned a status of SD, follow-up disease assessment must have met the SD criteria at least once after first dose at a minimum interval of 4 weeks.
- If the minimum time for SD is not met, best response will depend on the subsequent assessments. For example if an assessment of PD follows the assessment of SD and SD does not meet the minimum time requirement the best response will be PD. Alternative subjects lost to follow-up after an SD assessment not meeting the minimum time criteria will be considered not evaluable.

IIIf. Confirmation Criteria (recommended):

- To be assigned a status of PR or CR, a confirmatory disease assessment should be performed no less than 4 weeks (28 days) after the criteria for response are first met.

IIIg. Independent Review

Disease progression and response evaluations may be collected centrally during the study and may be reviewed or analyzed by an independent central reviewer. Details will be provided in the SPM.

References:

